### *17.3 Missing Data*

Every effort will be made to facilitate participants' completion of questionnaires and provision of blood samples. However, some missing data are inevitable. The magnitude and the reasons for missing data will be recorded and tabulated according to treatment group. If a large proportion of data is missing we will conduct sensitivity analyses using appropriate statistical methods (e.g., maximum likelihood, multiple imputations). If the estimates are similar to the ones obtained from the simpler analysis of only complete cases, we will report the complete-case analysis results.

### *17.4 Statistical analysis*

#### *17.4.1 Aim 1: Feasibility and adherence*

Our primary aim is to evaluate the feasibility of delivering a Mediterranean Diet patients undergoing chemotherapy. Despite us providing food to participants, we expect that there will be variability in dietary intake in the Mediterranean Diet arm due to participants not liking the taste of the meal(s), inconvenience, social barriers (e.g., eating out with friends, family, colleagues), cravings, symptoms such as nausea and diarrhea, etc. Adherence will be based on consumption of key dietary components (e.g., fruits, vegetables, olive oil, fish) and avoidance of red meat, sweet or carbonated beverages, and commercial sweets and pastries. Success will be deemed if >70% of participants who consent complete the study and if >70% of participants in the intervention arm improve their Mediterranean Diet score from pre- to post-intervention. Adherence to the provided diet will yield 13 out of 14 points on the 14-item scale (1 point for consumption of wine). The Mediterranean Diet score is commonly used in epidemiological studies to assess the relation between adherence to the Mediterranean Diet and prediabetes, metabolic syndrome, inflammation, etc. Between arm difference in Mediterranean Diet score will be evaluated by two-sample t-test.

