## 1. Purpose of the study

In this study, we will assess the feasibility of delivering an 8-week Mediterranean Diet intervention as well as the intervention's preliminary efficacy on cancer-related fatigue among patients undergoing chemotherapy, compared to usual care. In the first 4 weeks of the intervention, we will provide the participants with food and educate them on the principles and components of the Mediterranean Diet, while in the second 4 weeks participants will prepare their own food. In addition, we will evaluate changes in metabolism and mitochondrial function during 4 weeks of chemotherapy and determine how adherence to a Mediterranean Diet modulates these changes during these 4 weeks. These data will inform the design of a larger randomized clinical trial that evaluates the effects of the Mediterranean Diet vs. a behavioral control on cancer-related fatigue.

Aim 1: to evaluate the feasibility of delivering a Mediterranean Diet intervention, as measured by adherence at both 4 weeks and 8 weeks.

Aim 2: to evaluate the preliminary efficacy of a Mediterranean Diet vs. usual care to prevent cancer-related fatigue among patients with cancer undergoing chemotherapy, as assessed using the FACIT-F.

Mechanistic Aim: to evaluate the effects of the Mediterranean Diet on mitochondrial function (i.e., mitochondrial stress test) and blood-based metabolic biomarkers (e.g., fasting blood glucose, insulin).

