### **4. Study design**

#### *4.1 Brief description and specific aims*

This will be a feasibility pilot randomized controlled trial performed at a single site. We will recruit 42 patients with cancer who are beginning a chemotherapy regimen and randomize them 2:1 to the intervention group or usual care (28 in the intervention arm and 14 in the usual care arm). The uneven allocation serves to improve recruitment, as some patients are disappointed to be assigned to the usual care arm, and allows us to get more information about the intervention. This will be an open label study (due to the nature of the intervention it is not possible to blind participants, and due to the active involvement of the PI in data acquisition, it is not feasible to blind the PI). At baseline, participants will complete an on-study form that includes demographics and clinical characteristics. They will complete a 3-day food record (ideally from two weekdays and one weekend day), a fasted blood draw, and several questionnaires [i.e., 14-Item Mediterranean Diet Assessment Tool, Functional Assessment of Chronic Illness Therapy – Fatigue (FACIT-F), Aerobics Center Longitudinal Study (ACLS) physical activity questionnaire, Brief Fatigue Inventory (BFI), 27-item Symptom Inventory, Functional Assessment of Cancer Therapy-Cognition (FACT-Cog), Brief Pain Inventory (BPI), Insomnia Severity Index (ISI)]. For the duration of the study, all participants will complete a daily diary that includes their average fatigue level that day. For 4 weeks, we will provide participants in the intervention group with food based on the Mediterranean Diet. We intend this food to be substituted or supplemented with other food of the patients' choosing, though we encourage participants to comply with the Mediterranean Diet for all meals and snacks. During this time we will also provide education regarding the principles and composition of the Mediterranean Diet and how to effectively implement it at home. This education will include materials that encourage behavior change to inspire motivation and adherence to the diet. At 4 weeks, participants will undergo a mid-point evaluation where they will complete the same assessments as at baseline except for the on-study form. For weeks 5-8, participants in the intervention group will be encouraged to follow the Mediterranean Diet though we will not provide food. During the 8-week intervention, we will be in contact with participants in both groups to monitor adverse events and discuss any barriers to consuming the diet (in the intervention group). At 8 weeks, participants will repeat the assessments and undergo an exit interview, which will last approximately 15-30 min. Participants will receive \$20 total to complete baseline and post-intervention measures and those in the intervention group will receive free meals for 4 weeks. Those in the usual care group will be offered the intervention materials and one week of meals *gratis* at the conclusion of the study.

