
Intervention: For the first 4 weeks, those in the intervention arm will receive three meals per days compliant with the Mediterranean Diet. These meals will provide approximately 1,600 kcal/day (range 1,200-2,000 kcal/day) and will be evaluated by a registered dietitian with experience with patients with cancer (e.g., [name], RD, MPH, or [name], RD) for appropriateness and nutrient adequacy. We will encourage participants to supplement the provided food with food of their choosing so as to satisfy hunger and thirst; the amount of food that is supplemented will vary greatly due to each individuals' nutrient needs, and we encourage that all food be compliant with the Mediterranean Diet. During this time participants will receive education on the principles and components of the Mediterranean Diet. This will include a phone- or computer conferencing-led education session, information packet, and cookbook, all of which were designed specifically for this study.

The questionnaires will be completed via Research Electronic Data Capture (REDCap) or via paper-and-pencil (participants' choice); the food record and daily diary will be completed on paper. They will be scored and entered into a secure database by the study team. Preliminary efficacy of the intervention on cancer-related fatigue will be assessed using the FACIT-F as a primary endpoint, and also via the BFI and symptom inventory. Adherence will be determined using the 14-Item Mediterranean Diet Assessment Tool. Blood will be collected and used immediately for real-time respiration assay on T cells, sent for analysis at UR Labs, and/or processed and stored at -80°C in the CCPL for later assays.

Specific aims:

Aim 1: to evaluate the feasibility of delivering a Mediterranean Diet intervention, as measured by adherence at both 4 weeks and 8 weeks.

*The hypothesis is that those in the Mediterranean Diet group will score higher on the 14-Item Mediterranean Diet Assessment Tool at 4 weeks and 8 weeks.*

*We will consider the feasibility of the intervention successful if >70% of participants who consent complete the study and if >70% of participants in the intervention group improve their Mediterranean Diet score at least one point from baseline to 4 weeks and baseline to 8 weeks.*

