### 4.4 Study outcomes/endpoints

#### *4.4.1 Aim 1: Feasibility and adherence*

The primary aim of our study is to assess feasibility of implementing a Mediterranean Diet intervention. Feasibility will be determined by our ability to recruit participants to the study and have them complete the intervention. Our goal is that at least 70% of participants in each group complete the 8-week intervention including 8-week assessments.

1. 14-item Mediterranean Diet assessment: As part of Aim 1, we will assess the adherence of the participants to the diet. Adherence will be assessed primarily from the 14-item Mediterranean Diet assessment tool that is used commonly in the literature, mostly for epidemiological studies but also for clinical trials. We will ask participants to report their dietary habits over the last week. Questions include: ‘How many servings of fruit do you consume per day?’, ‘How many sweet or carbonated beverages do you consume per week?’, and ‘How much olive oil do you consume on a given day?’ We will deem a participant adherent if they show an improvement in score of at least 1 point from baseline to 4 weeks and baseline to 8 weeks. This cut-off has been established in the literature to be clinically relevant.

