### 8.2.7 Schedule of assessments

Baseline assessments will optimally be collected before the first infusion of chemotherapy, though assessments will not delay chemotherapy. Baseline assessments after chemotherapy is initiated is permissible as long as the patient has at least 6 more weeks of chemotherapy. 4-Week assessments will occur approximately during week 4 (during week 3-5); 8-week assessments will occur approximately during week 8, the last week of the intervention (week 7-9). However, this may be adjusted to accommodate factors such as the participant or researcher's schedule. Because of the immediate and transient effects that chemotherapy has on fatigue, we will aim to have assessments at least 3 days after an infusion. Optimally, the post-intervention assessments will occur during the last week of the intervention, while the participant is still on the diet, so that we can probe metabolic markers that may change quickly after cessation of the diet. **Table 3** describes two common chemotherapy regimens, but others exist and we will work around clinic activities to collect assessments.

Study Week	0	1	2	3	4	5	6	7	8
Study activities	Consent, Baseline assessments				4-week assessments				8-week assessments
Infusion number (for patients on biweekly regimens)		1		2		3		4	
Infusion number (for patients on weekly regimens)		1	2	3	4	5	6	7	8
Infusion number (for patients on an every 4-week regimen)		1				2			
Infusion number (for patients on an every 3-week regimen)		1			2			3	

**Table 3.** Schedule of chemotherapy infusions and study activities for two example chemotherapy regimens.

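### Section 17.4.1 judges adherence success on one pre-to-post comparison, whereas 4.1 and 4.4.1 require the gain at both week 4 and week 8

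*Combined protocol and SAP*

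**What the plan says.** Section 1 sets Aim 1 as feasibility "as measured by adherence at both 4 weeks and 8 weeks", and 4.1 repeats this. Section 4.1 then gives the success rule: ">70% of participants in the intervention group improve their Mediterranean Diet score at least one point" "from baseline to 4 weeks and baseline to 8 weeks", alongside a completion criterion. Section 4.4.1 deems "a participant adherent if they show an improvement in score of at least 1 point from baseline to 4 weeks and baseline to 8 weeks".

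The analysis section, 17.4.1, words the success rule differently. Adherence succeeds "if >70% of participants in the intervention arm improve their Mediterranean Diet score" "from pre- to post-intervention". Week 4 is not named, and neither is the one-point minimum.

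The term post-intervention has no formal definition, but section 8.2.7 says: "Optimally, the post-intervention assessments will occur during the last week of the intervention". The same section identifies that week as week 8, and 4.1 describes the 4-week visit as the middle of the intervention.

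**The concern.** Sections 4.4.1 and 17.4.1 both call feasibility the primary aim, and section 1 says the results will inform a larger trial. The adherence criterion is thus a decision rule, and the plan states it in two ways that can disagree on the same data. If this is left open, the choice between them could be made after the scores are known.

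The two visits also test different things. Food is supplied in weeks 1 to 4. After that: "For weeks 5-8, participants in the intervention group will be encouraged to follow the Mediterranean Diet though we will not provide food". Week 4 is also the visit of the primary fatigue endpoint (17.1, 17.4.2). Under 17.4.1 the adherence verdict would place no requirement on the visit at which the fatigue effect is estimated.

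**Working it through.** **Rules compared**

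| Section | Comparisons | Minimum gain | Unit of the 70% |
|---|---|---|---|
| 4.1 | Baseline to week 4 and to week 8 | 1 point | Group; per visit or per participant not stated |
| 4.4.1 | Baseline to week 4 and to week 8 | 1 point | Defines an adherent participant; no 70% attached |
| 17.4.1 | Pre to post (week 8 by 8.2.7) | Not stated | Group |

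Nothing else in section 17 restores a week-4 adherence criterion. Section 17.4.4 uses the week-4 diet score only for exploratory correlation with fatigue.

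**Can the rules disagree?** There are 28 participants in the intervention arm (4.1). More than 70% means more than 0.70 × 28 = 19.6, so at least 20. Suppose 21 improve at week 8: 21/28 = 75%, which meets 17.4.1. If only 18 improved at week 4, 18/28 = 64% misses 4.1 on either reading. If 18 improved at both visits but at least 20 did so at week 4, the per-visit reading passes and the participant-level reading fails.

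**How likely is a different verdict?** The plan has no figure to reproduce: it gives neither improvement rates nor the correlation between visits. All rates here are assumptions. Let p4 and p8 be the true proportions improved at each visit and b the proportion improved at both.

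- 17.4.1: P(X ≥ 20), X ~ Binomial(28, p8).
- Participant-level: P(X ≥ 20), X ~ Binomial(28, b).
- Per visit: the multinomial probability, over both / week 4 only / week 8 only / neither with cell probabilities b, p4 − b, p8 − b, 1 − p4 − p8 + b, that each visit has at least 20 improvers.

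Results for n = 28 with no loss:

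| p4 | p8 | b | 17.4.1 | Per visit | Participant-level |
|---|---|---|---|---|---|
| 0.80 | 0.80 | 0.64 (independent visits) | 0.91 | 0.83 | 0.27 |
| 0.80 | 0.80 | 0.70 | 0.91 | 0.84 | 0.53 |
| 0.80 | 0.80 | 0.75 | 0.91 | 0.86 | 0.75 |
| 0.90 | 0.80 | 0.75 | 0.910 | 0.909 | 0.75 |
| 0.75 | 0.85 | 0.70 | 0.98 | 0.74 | 0.53 |
| 0.90 | 0.90 | 0.84 | 0.999 | 0.998 | 0.97 |

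With p4 = p8 = 0.80, the three rules converge at 0.91 as b approaches 0.80, when the same people improve at both visits.

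**Denominator.** Sections 4.2 and 17.1 expect about 22 evaluable in this arm. Among those assessed, the cut-off is 16 of 22 (0.70 × 22 = 15.4). If 16 to 19 are adherent, that is 73% to 86% of the 22 assessed but 57% to 68% of the 28 randomised, which are opposite verdicts. If all 28 count and only 22 are assessed, success needs 20 of the 22. With b of 0.70 to 0.75, P(X ≥ 20), X ~ Binomial(22, b), is 0.02 to 0.06. The same denominator would also hurt the 17.4.1 rule: at p8 = 0.80, P(X ≥ 20), X ~ Binomial(22, 0.80), is 0.15.

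**The case against.** The best defence is that 17.4.1 is shorthand for a rule already given in full in 4.1, and that week-4 scores are collected anyway (8.2.8). That limits the harm, but it does not tell the analyst which sentence decides. On any meaning of post-intervention, 17.4.1 gives one comparison where 4.1 gives two.

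The second defence concerns size, and it largely stands. The only other 70% adherence rule is in 4.1, and it can be read per visit. On that reading the change is modest. The design also points to week 4 as the stronger visit, since food is supplied then and section 4.6 says provision is meant to raise adherence. In that case (0.90 and 0.80) the gap is 0.910 against 0.909. A large per-visit gap needs week 4 to be the weaker visit.

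Three stronger readings are not supported:

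- A reader might take the fall from 0.91 to 0.53–0.75 as the effect of omitting week 4. It belongs only to the participant-level reading, which 4.4.1 supports but does not tie to the 70%.
- A reader might think the missing one-point minimum loosens the rule. If items score whole points, as the 13-of-14 remark in 17.4.1 suggests, any improvement is at least one point.
- A reader might see a second contradiction in completion: more than 70% of those consenting (4.1, 17.4.1) against at least 70% in each group (4.4.1). The latter is stated as a goal and can coexist with the pooled success rule.

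On the denominator, 17.2 keeps all randomised participants in their allocated arm, and 17.3 requires missing data to be tabulated by group but allows complete-case reporting. Neither says what the adherence proportion is divided by.

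**Conclusion.** The inconsistency is real and lies in the current text: the analysis section omits a visit that the aim, its success rule and the definition of an adherent participant all include. That the same data can pass one rule and fail the other follows from the wording and needs no assumption beyond reading post-intervention as week 8.

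The practical size is uncertain. It runs from almost nothing (high adherence, the same people improving at both visits, or a per-visit rule with week 4 the stronger visit) to a large drop in the chance of success under a participant-level rule when different people improve at the two visits. All the probabilities rest on assumed rates.

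The effect is confined to the adherence verdict. The FACIT-F estimate, its test and the sample size do not depend on it. The point should be fixed, but it does not threaten the trial.

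**What to change.** Before data review:

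1. Replace the adherence criterion in 17.4.1 with that of 4.1: more than 70% of the intervention arm with a gain of at least 1 point at week 4 and at week 8.
2. State in both sections whether the 70% applies to participants who gain at both visits, which the 4.4.1 definition supports, or separately at each visit.
3. Name one deciding denominator, all randomised or those assessed, and report the other as a sensitivity result.

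This changes wording only, since the data are already planned. The cost is a rule harder to meet than the one now in 17.4.1. In the case with 80% improving at each visit, 70% to 75% at both, n = 28 and no loss, the chance of success goes from 0.91 to 0.84–0.86 per visit or 0.53–0.75 per participant. It would be far lower if all 28 randomised form the denominator and only about 22 are assessed, so items 2 and 3 should be settled together.

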#### *4.3.1 Mediterranean Diet intervention*

The first 4 weeks of the intervention we will provide food as well as a Mediterranean cookbook and tips to follow a Mediterranean Diet in the home. The menu will be based on the Mediterranean Diet Pyramid (**Fig. 2**) and the Mediterranean Exchange List developed by Djuric et al. (2008) for implementation in research. These guidelines include categories of foods (e.g., dark green vegetables, high-monounsaturated fatty acids), goal amounts of each category, and foods that fall into each category. Consumption of all of the food provided to the participant will cause them to be adherent with the Mediterranean Diet intervention, and foods can be substituted with the participant still being adherent. Although red wine is recommended as part of the Mediterranean Diet, we will not recommend or provide any alcohol due to lack of research regarding the benefits/drawbacks of alcohol consumption on the efficacy of the chemotherapy or supportive care outcomes. The menu will include meals every day for one week (7 breakfasts, 7 lunches, and 7 dinners) plus snacks, and then the menu will be repeated four times to span the four-week period. The provided food will be approximately 1,600 kcal/day (1,200-2,000 kcal), though participants will be encouraged to consume additional food to avoid hunger. These diets have been developed in conjunction with [name], [name], and their staff at the Highland Hospital’s Weight Management & Lifestyle Center (NCT03045289). Their team has successfully developed and executed a plant-based diet intervention and is developing a Dietary Approaches to Stop Hypertension (DASH) diet intervention (NCT04048642). The Mediterranean Diet menu will be assessed for completeness and safety in conjunction with a registered dietitian (e.g., [name], RD; [name], RD).

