#### *17.4.4 Exploratory analyses*

In an exploratory analysis, we will correlate Mediterranean Diet score with patient-reported fatigue using the FACIT-F fatigue score at 4 weeks and 8 weeks. We expect that the majority of participants will improve their Mediterranean Diet score, and that 4 and 8 week scores will range from 5-14 in the intervention group (higher is better). We expect that the fatigue subscale of the FACIT-F will range from 0-43 out of 52 based on a historical dataset (Kleckner et al.; a higher score indicates less) and that FACIT-F total scores will range from 44-160 out of 160^161 (higher is better well-being). We will also assess correlations between baseline Mediterranean Diet score (proxy for improvement in diet quality) and change in fatigue to evaluate the influence on baseline diet on the development of fatigue. Further, we will assess the change in the Mediterranean Diet score and the change in fatigue to see if a greater shift in diet led to a greater prevention of fatigue.

Other measures collected via patient-reported outcome questionnaires (e.g., BFI, Fact-Cog) will be analyzed using similar methodology as outlined in the Aim 2 (FACIT-F score analysis).

**Because of the small sample size in this study and the resulting low statistical power, these secondary and exploratory analyses will be interpreted very cautiously and only used to aid in the designing of a study for our larger trial and generation of new hypotheses.**

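### The adherence criterion scores a wine point that the intervention does not deliver, and with a 1-point threshold that item alone can decide a borderline participant

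*Combined protocol and SAP*

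**What the plan says.** Section 4.3.1 describes the diet and says of wine that "we will not recommend or provide any alcohol". Section 17.4.1 draws the consequence for the score: "Adherence to the provided diet will yield 13 out of 14 points on the 14-item scale", with "1 point for consumption of wine" accounting for the difference.

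The adherence rule is in Section 4.4.1: "We will deem a participant adherent if they show an improvement in score of at least 1 point", measured from baseline to 4 weeks and from baseline to 8 weeks. On the reporting period it says "We will ask participants to report their dietary habits over the last week". Section 4.1 makes this one of the two feasibility conditions: ">70% of participants in the intervention group improve their Mediterranean Diet score at least one point". Section 17.4.1 repeats the 70% condition without naming the 1-point size or the two time points. On a score that moves in whole points, any improvement is at least 1 point. The same section compares the score between arms with a two-sample t-test.

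Section 17.4.4 expects that "4 and 8 week scores will range from 5-14 in the intervention group". A score of 14 can be reached only if the wine item counts. No section removes the wine item from the adherence score, holds it at its baseline value, or plans an analysis without it.

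**The concern.** The criterion is meant to show whether participants took up the diet that the study offers. One of its 14 items lies outside that diet by design. This would matter little if the threshold were several points, but it is exactly the size of one item, so an item unrelated to the intervention can settle the call on its own.

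The comparison with usual care gives no protection. The 70% condition is judged within the intervention arm, so a change in drinking common to both arms does not cancel. Section 8.2.7 prefers baseline before the first infusion. For those participants the change score spans the start of chemotherapy, when intake may shift for reasons unrelated to the diet. The condition is half of the success rule for the primary aim.

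**Working it through.** **Inputs.** 14 items, 1 of them wine (17.4.1). Threshold of +1 at both 4 and 8 weeks (4.4.1). Success if more than 70% of the intervention arm meet it (4.1). 28 randomized to the intervention (4.1), 22 expected evaluable (17.1). Baseline score below 10, because scores of 10 or more are excluded (Section 5).

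**The plan's own figure.** 14 − 1 = 13, as stated in 17.4.1.

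**The rule at one assessment.** Total change = change on the 13 other items + change on the wine item. The participant passes if the total is at least +1.

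| Change on 13 other items | Wine point lost | Wine unchanged | Wine point gained |
|---|---|---|---|
| −1 | −2, no | −1, no | 0, no |
| 0 | −1, no | 0, no | **+1, yes (reversed)** |
| +1 | **0, no (reversed)** | +1, yes | +2, yes |
| +2 | +1, yes | +2, yes | +3, yes |

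Two of the 12 combinations differ from the call based on the 13 other items. At +2 or more, or at −1 or less, wine makes no difference.

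**Both assessments.** Because 4.4.1 requires the gain at 4 and at 8 weeks, losing the wine point at either one is enough to fail a participant who stands at exactly +1 elsewhere at that assessment. The opposite error is harder to make. A participant with no change on the other items must gain the wine point and hold it at both.

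**Room for gains.** If the screening tool scores wine, a participant who enters with the wine point has at most 9 − 1 = 8 of the 13 other points. At least 13 − 8 = 5 remain available, and 2 are needed if the wine point is lost. Full uptake of the provided diet would give at least +5 − 1 = +4.

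**The 70% condition.** 0.70 × 22 = 15.4, so 16 are needed: 16/22 = 72.7%, 15/22 = 68.2%. If all 28 are counted, 0.70 × 28 = 19.6, so 20 are needed: 20/28 = 71.4%, 19/28 = 67.9%.

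**Illustration only.** The documents give neither drinking rates nor the scoring cut-off of the wine item. Assume that 5–30% lose the wine point and that 10–40% of those stand at exactly +1 elsewhere. The observed rate then falls by between 0.05 × 0.10 = 0.5 and 0.30 × 0.40 = 12 percentage points. The table shows the binomial probability of meeting the 70% condition at one assessment, assuming a 13-item rate of 80%.

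| Net effect of wine on the rate | n = 22 | n = 28 |
|---|---|---|
| none (80%) | 0.87 | 0.91 |
| 5 points down (75%) | 0.70 | 0.75 |
| 10 points down (70%) | 0.49 | 0.53 |
| 5 points up (85%) | 0.96 | 0.98 |

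**The case against.** The strongest reply is that this is an open design choice. The plan states the 13-point ceiling, uses an established instrument, and cites a source for the 1-point cut-off. Section 5 accepts a similar trade-off for vegetarians, who forgo the fish point and can still be adherent. It is true that nothing is hidden. But the ceiling and the fish example concern the level of the score, whereas adherence is a change. A point never held at any assessment cancels out of a change score. A point gained or lost between assessments does not.

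The second reply is that the baseline cap leaves ample room for food gains, so only people who barely changed their diet are at risk. This stands and limits the point. It is weaker for weeks 5–8, when no food is provided and gains may be smaller.

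Third, the 5–14 range in 17.4.4 is an expectation in an exploratory section, not a scoring rule, and 17.4.1 names foods rather than wine as the basis of adherence. Both are fair. The food list is only by way of example, however, and 17.4.1 itself counts the wine point. Section 5 calls the screening questionnaire modified without saying how, which does not settle the matter. The 3-day food records give further dietary information but do not enter the criterion.

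A reader might go further and infer that the wine item will make a working intervention look infeasible, or that a definite share of participants will be misclassified. The documents support neither reading. They contain no drinking rates, gains of the wine point push the result the other way, and anyone who gains 2 or more points elsewhere is unaffected.

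**Conclusion.** The point holds as a matter of the scoring rule. The criterion includes an item that the intervention deliberately leaves out, and the 1-point threshold lets that item alone reverse the call when the other 13 items change by exactly 0 or exactly +1. The direction of the net error is unknown, and its size cannot be derived from the documents. The percentages and probabilities above depend on assumed rates and should not be read as estimates. What does follow from the plan's figures is that, near the threshold, one person decides the outcome: 16 versus 15 of 22, or 20 versus 19 of 28. The sample size is not affected. This is a minor point, worth acting on because the remedy costs so little.

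**What to change.** In Sections 4.1, 4.4.1 and 17.4.1, define the adherence gain and the between-arm score comparison on the 13 non-wine items at baseline, 4 weeks and 8 weeks. Report the full 14-item result alongside as a sensitivity analysis. State that the 1-point cut-off was cited for the 14-item score and is being carried over to 13 items. Leave the eligibility screen as it is, but say which version of the questionnaire is used for adherence, given that Section 5 calls the screening version modified.

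The cost is about a sentence in each section. The item responses are already collected, so no new data, visits or participants are needed. The change is best made before follow-up scores are examined. The downside is slightly less direct comparability with published 14-item results, which the sensitivity analysis largely covers.
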